## **Protocol Organization for DF/HCC Protocol 16-477**

The protocol document contains the study procedures for the HOPE Trial and the SMART Study. The SMART Study is a sub-study of the HOPE Trial. Both studies evaluate *an almost identical intervention* using a Fitbit device and smartphone app(s) with the goal of improving quality-of-life for women with gynecologic cancers. However, the studies are designed to assess different research questions, and there are slight variations in the interventions being administered: the HOPE Trial is a randomized controlled trial designed to test changes in health-related quality of life at an NCI-designated Comprehensive Cancer Center (DFCI), while the SMART Study is a single-arm study designed to test the feasibility and acceptability of a combined intervention (Fitbit device and two smartphone apps) in NCORP community oncology sites.

Because the interventions tested are similar and only minor variations exist in study procedures (e.g., in timings of outcomes assessments), the studies are being reviewed under one IRB protocol at Dana-Farber Cancer Institute.

The HOPE Trial is being conducted only at Dana-Farber Cancer Institute. *No outside sites are participating in the HOPE Trial.* The HOPE Trial (Phase 2) is a four-arm randomized controlled trial testing Fitbits and a smartphone app. The primary endpoint of Phase 2 of the HOPE Trial is health-related quality of life.

The SMART Study is being conducted only at outside community oncology sites. *Dana-Farber Cancer Institute is not enrolling patients in the SMART Study.* The SMART Study is a single-arm study testing a Fitbit and two smartphone apps (Beiwe and SMART). Primary endpoints for this study are feasibility and acceptability of the intervention in the community oncology sites.

[figure not shown]
To facilitate protocol implementation and regulatory review at both Dana-Farber and outside sites, this document is separated into two sections. Part 1 is the protocol for the HOPE Trial conducted at Dana-Farber only; Part 2 is the protocol for the SMART Study conducted at community oncology sites only. Lettered appendices (Appendices A-Z and AA) correspond with the HOPE Trial; numbered appendices (Appendices 1-24) correspond with the SMART Study.

The HOPE Trial section begins on p.2 of this document. The SMART Study section begins on p. 41 of the document.

[figure not shown]

## 1.0 INTRODUCTION

### 1.1 Overview

The goal of palliative chemotherapy is to reduce cancer patients' symptoms and extend survival. Yet, oncologists' methods of monitoring patients' symptoms are underdeveloped. Studies show that clinicians consistently miss more than half of cancer patients' symptoms, even in clinical trials that mandate collection of treatment toxicities. This may be because clinicians see patients at fixed time points (e.g., every 3 weeks linked to chemotherapy infusions) when patients have already recovered from their last treatment. Additionally, patients may underreport symptoms in clinical settings or have difficulty estimating their activity levels, hindering oncologists' ability to accurately assess patients' symptoms and/or performance statuses. The moments between visits—when patients are at the highest likelihood of experiencing toxicities—are more likely to contain meaningful information about patients' symptoms and activity levels in the *real world*. Mobile health technologies (e.g., smartphones and accelerometers) offer novel methods for assessing patients' symptoms and activity levels and opportunities to intervene to reduce suffering.

The first goal of this study is to adapt and refine an existing smartphone app, paired with a wearable accelerometer, to assess patients' symptoms in a population of patients with gynecologic cancers receiving palliative chemotherapy. An existing app will be customized to collect patient-reported toxicities using the Patient Reported Outcome (PRO) version of the Common Terminology Criteria for Adverse Events (PRO-CTCAE) and offer patients feedback about how to manage their symptoms. Patient symptoms will be risk-stratified. Patients with low-risk toxicities (grades 1 & 2) will receive tailored educational information, while patients with serious toxicities (grades 3 & 4) will receive alerts to call their clinician. Patients will also receive a graphical summary of their symptoms to share with clinicians during office visits. In first phase of the study we will conduct an initial assessment of the app with a diverse group of 10 patients to refine the app and test two different wearable accelerometers (i.e. Fitbit Zip and Fitbit Charge 2) before pilot testing. The wearable accelerometers will be used as a quantitative measure of patient performance status, and to detect severe symptoms that may impact patients' average daily steps (e.g., abdominal pain, nausea, diarrhea). Patients will also be provided with a graphical summary of their average daily steps to share with clinicians.

The second goal of this study is to conduct a pilot randomized controlled trial (RCT) of the smartphone app and/or wearable accelerometer (i.e. Fitbit Zip or Fitbit Charge 2) to assess the feasibility, acceptability, and preliminary efficacy of our intervention. During the second phase of the study, we will conduct a 4-arm pilot RCT in 100 patients with gynecologic cancers receiving palliative chemotherapy to establish preliminary effect sizes. Participants will be randomized to: 1) Fitbit+active app, 2) Fitbit+passive app, 3) Active app, or 4) Passive app. We hypothesize that the use of a Fitbit and an active app designed to assess PRO symptoms and deliver tailored advice to cancer patients receiving palliative chemotherapy will reduce the use of high-intensity health care (i.e., unplanned infusion appointments, emergency room visits, and hospitalizations), compared with a Fitbit + passive app, Active app, or Passive app alone. We also hypothesize that patients randomized to the Fitbit + active app will have improved health-related quality of life (comparing the baseline and 6-month EuroQol EQ-5D), compared with other groups. Additionally, we expect that data collected from the wearable accelerometers and smartphone accelerometers (via passive app) will be significantly correlated with each other, and will provide quantitative measures that are correlated with patients' performance status.

We expect that the results of this pilot RCT, which is supported by the National Cancer Institute, National Palliative Care Research Center, and the Dana-Farber Cancer Institute Department of Medical Oncology, will provide a low-cost, scalable system to assess patients' symptoms, address low-risk toxicities, and alert clinicians when patients have toxicities that require intervention with the goal of reducing patient suffering and the use of high-intensity, hospital-based health care. Upon completion of this project, we will be well positioned to test the efficacy of this intervention in a full scale RCT.

## 1.2 Background and Rationale

There is substantial evidence that oncologists' miss up to half of cancer patients' symptoms, even within the context of clinical trials, which mandate structured reporting of symptoms and treatment toxicities. Evidence suggests that the integration of PROs into routine cancer care results in more efficient symptom assessment, improved communication and continuity of care, better quality of life, lower health care utilization rates, and superior quality-adjusted survival, compared with usual care. This is important because while prior studies have demonstrated that the early integration of palliative and oncologic care improves patients' quality of life and survival, health systems are facing a serious workforce shortage of trained palliative care providers. Low-cost, scalable systems designed to assess patients' symptoms, address low-risk toxicities, and alert clinicians when patients are in danger are urgently needed.

Several studies have demonstrated that cancer patients with serious illnesses are willing to report their symptoms using technology, including tablets and web-based systems, even close to the end of life. One large study of cancer patients found that nearly 70% of patients wanted to receive information and support about their disease through the internet. Another demonstrated that the use of a web-based system to assess PROs in patients with advanced cancer, combined with automated clinical alerts, resulted in better health-related quality of life, fewer emergency room visits and hospitalizations, and superior quality-adjusted survival, compared with usual care. Recently Denis et al. reported that the use of a web-based system to assess PROs weekly in patients with high-risk, non-small cell lung cancer resulted in earlier detection of symptomatic disease recurrences, earlier institution of supportive care, better patient quality of life, and improved overall survival, compared with routine clinical assessments. Researchers have not examined similar endpoints in patients with gynecologic malignancies, to our knowledge, but one small study found that chemotherapy toxicity reporting was feasible in women with gynecologic cancers using a web-based system, and that use of this system improved patient recall of symptoms at follow-up visits, communication with physicians and nurses, and patients' self-efficacy.

To date, however, most studies have focused on collecting patient-reported symptoms during clinic visits that are frequently tied to chemotherapy infusions. Two key limitations to this approach are: 1) patients have often already recovered from many treatment-related toxicities and 2) it relies upon patients' retrospective recall of events, which are often inaccurate. Few studies, to our knowledge, have performed *real time* and *real world* assessments of cancer patients' symptoms and activity levels in daily life.

Smartphone-based interventions are a low-cost, scalable tool for measuring and modifying health behaviors. In 2015, 64% of Americans owned a smartphone and more than 33% reported relying upon it as their sole tool for accessing the Internet, particularly among low-income and racial/ethnic minority populations. Mobile health interventions have demonstrated efficacy in assessing pain, monitoring psychiatric diseases, increasing medication adherence and improving other important clinical outcomes (e.g., systolic blood pressure, and body mass index).

Smartphones are capable of collecting two types of information: 1) "active data" which require patients' involvement (e.g., taking surveys; please see Figure) and 2) "passive data" which are collected without the patients' involvement (e.g., accelerometer data or spatial location). One of the advantages of using smartphones is that they can leverage sophisticated surveying techniques to generate personalized assessments, eliminating questions that have a high likelihood of being irrelevant and therefore reducing the survey burden upon participants. Smartphones can also be used to provide patients with real time active feedback for symptom management or to notify them that their symptoms are serious and require immediate attention.

**Figure 1**

Please rate the following statements.

I have been sleeping well

I would be better off dead or hurting myself

I have trouble concentrating

To date, few studies have examined the use of mobile phone-based interventions in patients with cancer. Similarly, few have collected quantitative measurements of cancer patients' activity levels for extended time periods. This study is innovative because it will harness a validated app, which is being piloted in psychiatric, neurological, and surgical patients in the Partners HealthCare system, to collect **passive** data from patients (e.g. accelerometer, spatial location, and sleep data) and **active** data, including patients' symptoms and treatment toxicities. The app has been tailored to categorize patient symptoms as low or high-risk, based upon clinical algorithms, and provide them with tailored advice to help manage their symptoms in *real* time in the *real* world. It is also innovative because it will enable clinicians to better understand patients' symptoms in the time between visits. We expect this study will increase the frequency of discussions about patients' symptoms between patients and providers. We also expect that this formative development work and early feasibility trial will set the stage for launching a broad portfolio of mobile-health intervention studies to improve seriously-ill cancer patients' symptoms, performance statuses, and clinical outcomes.

Like smartphones, wearable accelerometers (e.g. Fitbit Zip and Fitbit Charge 2) offer another novel means for collecting *real world* data to objectively measure patients' performance statuses. Patients' retrospective reports of activity levels are often inaccurate or imprecise. Without accurate information, oncologists may have difficulty objectively assessing patients' performance statuses, and may underestimate patients' symptom burdens and chemotherapy-related toxicities. Indeed, oncologist estimates of patients' performance statuses are only moderately correlated with one another and weakly correlated with patient estimates, but improve when clinicians and patients participate in "shared" reporting of patients' toxicities and performance statuses.

Wearable accelerometers are devices that track users' energy expenditures, the amount and intensity of physical activity, and sedentary behavior. They offer cost-effective, user-friendly, and objective measurements of patients' free living patterns. A few studies have piloted wearable accelerometers in adult cancer patients undergoing stem cell transplants (HCT) or treatment for colorectal, gastrointestinal, breast, and lung cancers. Results from one study of adult patients undergoing HCT who wore accelerometers over an 8 week period found that patients' reports of severe symptoms, impaired physical health, and restrictions in activities of daily living were associated with statistically significant decrements in objectively measured steps, suggesting that this may be an independent, quantitative measure of quality of life and patient performance status. In this study of 32 patients undergoing HCT over a 4 week period patients' averaged 3,595 steps daily, and lower levels were significantly associated with an increased symptom burden. Although similar estimates are not available in patients with gynecologic cancers, to our knowledge, we expect that symptoms are likely to impact the amount of walking that patients can do and will therefore provide an independent measure of both patients' performance status and symptom burden.

In the second phase of this study all patients will have passive data collected via the app. We will compare the active version of the smartphone app (which collects passive data, surveys patients about their symptoms, and provides tailored symptom management advice) alone or paired with a wearable accelerometer against a wearable accelerometer or control in a four arm RCT (see study schema). This will enable us to examine whether the active smartphone app and wearable accelerometer improve patients' quality of life, compared with active smartphone app or the wearable accelerometer, and determine whether their effects are independent or additive. In addition, it will help us determine whether wearable and smartphone-based accelerometers can provide valid and reliable measures of patient performance status and treatment toxicities.

## 2.0 OBJECTIVES

### 2.1 Phase 1

Objective: Adapt and refine an existing smartphone app to assess patients' toxicities and activity levels in 10 patients with metastatic gynecologic cancers receiving palliative chemotherapy and compare two wearable accelerometers (Fitbit Zip and Fitbit Charge 2) for use in the pilot RCT.

- Hypothesis: Patients will be able to successfully recharge the Fitbit Charge 2 every 3-4 days, but will prefer the Fitbit Zip because it does not require recharging.
- Hypothesis: The use of a wearable accelerometer will provide a quantitative measure that is correlated with patient performance status, and decrements of >25% in average daily steps will be associated with worse patient-reported quality of life and physical health (measured by the PROMIS Global-10 items 2 and 3).

### 2.2 Phase 2

Objective: Conduct a four-arm pilot randomized controlled trial (RCT) comparing the Fitbit + active smartphone app, Fitbit + passive app, Active app, or passive app alone to assess the feasibility, acceptability, and preliminary efficacy of the intervention.

- Hypothesis: Use of a monitored wearable accelerometer/passive smartphone app will improve patients' health-related quality of life (comparing the baseline and 6-month EuroQol EQ-5D), compared with passive smartphone app alone.
- Hypothesis: Use of both the active smartphone app and a monitored wearable accelerometer will improve patients' health-related quality of life (comparing the baseline and 6-month EuroQol EQ-5D), more than the active smartphone app or wearable accelerometer/passive smartphone app alone.
- Hypothesis: Use of the active smartphone app and a monitored wearable accelerometer will reduce the use of high-intensity health care (i.e., unplanned infusion appointments, emergency room visits, and hospitalizations), compared with a monitored wearable accelerometer/passive app, active smartphone app, or passive app alone.
- Hypothesis: Use of the active smartphone app will decrease the number of patient phone calls and/or for symptoms, compared with a wearable accelerometer/passive app or passive app alone.
- Hypothesis: Patients' and oncologists' estimates of a patient's performance status will be more closely correlated in patients randomized to the monitored wearable accelerometers/passive app compared with the active smartphone app alone or the passive smartphone app alone.
- Hypothesis: Data collected from the wearable accelerometers and smartphone accelerometers (via passive app) will be significantly correlated with each other, and will provide quantitative measures that are correlated with patients' performance status and will be predictive of clinically significant events (hospitalizations, emergency department visits, and chemotherapy appointments)
- Hypothesis: The correlation between the wearable accelerometers and smartphone accelerometers (via passive app) will be higher in patients randomized to be encouraged to wear their smartphone at all times, and the predictive ability of the smartphone accelerometers for patients' performance status and

clinically significant events will be greater in in patients randomized to be encouraged to wear their smartphone at all times.

- Hypothesis: Participants will express more negative affect and anxiety related to their cancer experience in the weeks preceding scans, compared with the weeks when scans are not performed. This association will be moderated by participants' coping style (as measured by the brief COPE).

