### **5.21n Cancer Experience Question**

#### *About the cancer experience question*

On a weekly basis, participants will be asked one qualitative question about their cancer experience. We hope that this open-ended question will give patients an opportunity within the study to express additional concerns, emotions and experiences regarding their cancer that may not be adequately reflected in other study instruments. A large body of previous work has successfully asked cancer patients to share open-ended, qualitative measures of their emotional experiences (i.e. by writing in response to a prompt). However, to our knowledge, our study will be the first to examine whether these qualitative measures correspond with clinical outcomes measured in real time in the real world.

Using a question adapted from Stanton and colleagues' emotional expression study with breast cancer survivors, participants will be asked to describe their experience with cancer over the course of the previous week. Participants will be presented with the cancer experience question as an audio survey within the HOPE App once a week (see Appendix F for question text) and will record their answers into the microphone of their smartphone. The app reminds the participant to make a voice recording in the same way that it reminds the participant to take any other survey in the HOPE app: by making a notification appear in the phone. The participant does not need to make a voice recording immediately and may wait until she is in private to do so. The participant can make the audio recording in the app at any time after the notification appears, until the next audio recording reminder replaces it. Participants will spend up to 5 minutes on this question, depending on how much they wish to share. This question will be answered within the smartphone app at the baseline interview and symptom survey (once weekly).

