#### *Cancer experience question analysis plan*

We plan to analyze qualitative data from the cancer experience question using the Linguistic Inquiry and Word Count (LIWC) program, developed by James Pennebaker and colleagues and used widely in emotional expression literature with cancer patients and other populations. LIWC reads text and identifies which words are associated with psychologically-relevant categories, i.e. affect, cognitive processes, content dimensions, etc. Because the holistic nature of the responses may not be adequately captured by the word count approach of LIWC analyses, we also plan to perform a content analysis of the output from the cancer experience question with trained independent raters, examining categories of psychologically relevant content in the recordings. For Phase I, due to the limited sample size, analyses will be descriptive in nature. For Phase II, we plan to use multivariate analyses of covariance (MANCOVA) as primary statistical procedures, controlling for baseline values, on conceptually related groups of variables including physical health-related outcomes (i.e., symptoms and healthcare utilization), psychological adjustment as measured by other study instruments (i.e., quality of life and emotional acceptance), and psychological properties of participants' responses to the cancer experience question (i.e. positive and negative affect). We also plan to conduct preliminary multivariate analyses of variance for continuous variables and chi-squared analyses for categorical variables, on demographic variables, cancer-related parameters, and other relevant variables (e.g. quality of life) at baseline. If relevant, we will use the baseline values on these measures as covariates to control for nonsignificant chance variation between groups at baseline.

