## 5.22 Medical Chart Abstractions and Patient-Reported Medical Resource Utilization

### **5.22a Health/Treatment Information**

Participants' medical charts will be reviewed to abstract health and treatment related information, including disease site, comorbid health conditions, number of prior chemotherapy regimens, and time since diagnosis. Data will be recorded in the *Health/Tx Info* form (Appendix G).

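### No analysis in the plan, as described, estimates the scan-anxiety hypothesis: the one method named for the weekly responses, a baseline-adjusted MANCOVA, has no scan-week term, within-person structure or coping interaction

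*Combined protocol and SAP*

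**What the plan says.** **Hypothesis.** Part 1 (HOPE), section 2.2, expects participants to express more negative affect and anxiety about their cancer "in the weeks preceding scans, compared with the weeks when scans are not performed". It adds that coping style, measured by the Brief COPE, will moderate this association.

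**Outcome data.** Under section 5.21n the cancer experience question is asked at baseline and then weekly, as a voice recording in the app. Table 3 assigns it to arms 1 and 3 only. Recordings are scored with LIWC and by content raters.

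**Analysis.** For Phase 2, section 5.21n states: "we plan to use multivariate analyses of covariance (MANCOVA) as primary statistical procedures, controlling for baseline values". The variables listed include the positive and negative affect expressed in the responses. Preliminary baseline tests come with it: "We also plan to conduct preliminary multivariate analyses of variance for continuous variables and chi-squared analyses for categorical variables". On covariates it says: "If relevant, we will use the baseline values on these measures as covariates to control for nonsignificant chance variation between groups at baseline".

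**Scan dates.** The items that section 5.22a lists for chart abstraction include disease site, comorbid conditions, "number of prior chemotherapy regimens, and time since diagnosis". Section 5.22b lists treatments, visits, admissions and hospice referrals. Neither list mentions imaging.

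**The concern.** The hypothesis is about weeks, not participants. To test it, one must know which weeks precede a scan, compare scores between those and other weeks in the same women, and let the difference vary with coping style. The only inferential procedure named for these responses adjusts for baseline and refers to variation between groups. An analyst who followed it would obtain contrasts between groups of participants, or nothing on scans at all.

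At stake is a stated Phase 2 hypothesis. If its model, pre-scan window, outcome and coping score are all chosen after the data are seen, any positive result will be hard to interpret. If the named procedure is followed literally, the weekly data collected from the active-app women do not bear on the question.

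**Working it through.** The plan gives no alpha, effect size, standard deviation or power for this hypothesis, so there is no figure to reproduce. The check is mainly a comparison of sections.

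**1. What the hypothesis needs, against what is specified**

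| Needed | Where the plan stands |
|---|---|
| Repeated weekly scores | Collected in arms 1 and 3 (section 5.21n, Table 3) |
| Pre-scan-week indicator | Not in section 5.21n or sections 6.1 to 6.5; window not defined |
| Within-person structure | None described |
| Pre-scan x coping interaction | None described |
| Coping score | Brief COPE at baseline, ten subscales kept (section 5.21o); none chosen |
| Scan dates | Not among the listed items (5.22a, 5.22b); forms not in the text |

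The rest of the plan does not repair this. Section 6.1 lists anxiety as an additional clinical outcome, and section 6.4 analyses it in the same way as the EQ-5D, by arm. The GAD-7 is given only at study interviews (days 0, 30, 90 and 180), so it cannot supply a weekly contrast.

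The two categories in the hypothesis can also overlap: a week that precedes a scan may itself contain no scan.

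**2. Amount of data**

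- Women asked the weekly question: 25 + 25 = 50.
- Weeks per woman: 180 / 7 = 25.7.
- Ceiling: 50 x 180 / 7 = 1,286 recordings.

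Precision depends on the number of pre-scan weeks, which the documents do not give. Assume one pre-scan week per scan, a scan every 8 to 12 weeks, and 50% to 75% of recordings completed:

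- Full completion: 1,286 / 12 = 107 to 1,286 / 8 = 161 pre-scan recordings.
- With missed recordings: 107 x 0.50 = about 54 to 161 x 0.75 = about 121.

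**3. Illustration of the consequence (all inputs assumed)**

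Simulated data: 50 women, 26 weeks, scans every 8 or 12 weeks, within-person correlation 0.3 or 0.6, 50% or 75% completion, and a pre-scan shift of 0, 0.3 or 0.5 SD. Tests were at 5% two-sided.

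| Analysis | No shift | Shift 0.3 SD | Shift 0.5 SD |
|---|---|---|---|
| Within-person regression on a pre-scan indicator | rejects 4% to 6.5% | 67% to 99.8% | 97% to 100% |
| Baseline-adjusted MANCOVA, arm as factor | rejects 3% to 7% | 5% to 6% | 3% to 8% |

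The MANCOVA rate does not respond to the shift. With 300 runs per setting its simulation standard error is sqrt(0.05 x 0.95 / 300) = 1.3 percentage points, so 3% to 8% is its nominal level with noise.

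Two limits apply. Arm was chosen as the MANCOVA factor because the plan names none, so the flat rate follows from having no scan term. The shift was the same for every woman, so power would be lower if it varies between women. Power for the coping interaction was not examined.

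**The case against.** **The MANCOVA may never have been meant for this hypothesis.** Section 5.21n is a general plan for the cancer experience question and mentions neither scans nor coping. A reader might infer that the sponsor chose the wrong test for the scan hypothesis, and the documents do not support that. What stands is narrower: no analysis is specified for the hypothesis, and the only one named for its outcome does not fit as described.

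**Multivariate methods can handle repeated measures.** This is correct. The plan states no data layout, so it cannot be said that each woman is reduced to one row. A repeated-measures version with a scan-week factor and a coping interaction could test the hypothesis, but none is described.

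**Scan dates may be collected.** A reader might infer that they are not. Both abstraction lists are introduced as examples, and the forms (Appendices G and H) are not in the text. Charts are also reviewed around each study visit, so dates might be recoverable later. The point is one to confirm, not an established omission.

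**Covariate selection is a different issue.** Choosing baseline covariates after baseline tests does not cause the mismatch, and fixed baseline covariates matter little to a within-person week contrast. It remains a minor weakness of its own.

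**The stakes are low.** The hypothesis is the last bullet of section 2.2, is neither the primary endpoint nor among the six secondary outcomes, and belongs to a pilot. This limits the weight of the point but does not remove it, because the correction costs very little.

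**Conclusion.** The point holds in limited form. The scan-anxiety hypothesis is a comparison of weeks with a coping moderator, and nothing in the plan as described estimates it.

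The affected data are at most 50 women and about 1,290 recordings, on the planned 25 per arm and full completion over 180 days. The usable pre-scan weeks are far fewer: roughly 54 to 121 under the assumptions above. The power figures illustrate that the weekly data could be informative; they are not predictions for this trial.

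The documents do not show that the hypothesis is untestable with the data collected. They show that the analysis is not yet specified. The hypothesis is in effect exploratory, and the EQ-5D comparison, the sample size and the randomisation do not depend on it.

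**What to change.** For this hypothesis, replace the MANCOVA with a prespecified person-week linear mixed model in arms 1 and 3:

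- **Outcome:** one named weekly score, for example LIWC negative affect or anxiety.
- **Fixed effects:** a pre-scan-week indicator, study week, the chosen coping score, and the pre-scan x coping interaction.
- **Random effects:** a participant intercept and a pre-scan slope. Without the slope, uncertainty about the coping interaction can be understated. With only two or three pre-scan weeks per woman the slope may be hard to estimate, so name a fallback in advance, such as standard errors clustered by participant.
- **Definitions:** the length of the pre-scan window, how the scan week itself is classed, and which Brief COPE subscale or subscales represent coping style.
- **Missing recordings:** state how missed weeks, death and dropout are handled, and report completion separately for pre-scan and other weeks.

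Confirm that the chart abstraction forms capture scan dates, or add that field.

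Separately, fix any baseline covariates in advance and drop the preliminary baseline tests as a way of selecting them.

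The cost is plan wording, a few decisions on definitions, and at most one field in an abstraction the research assistant already performs. No new patient assessment is needed.
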